#### **Potential Benefits of the Proposed Research to Human Subjects and Others:**

There are several potential benefits to study participants. First, participants who receive SST may experience improvements in quality of life, mental health, physical functioning, and self-efficacy. Second, this study will provide data on the feasibility, acceptability of studying measures that capture physical and psychological resilience.

This program of research has the potential to meaningfully enhance the mental health, physical functioning, and overall well-being of older adults with late-stage lung cancer, change clinical practice, and substantively enhance the quality of life of patients.

#### **Importance of the Knowledge to be Gained:**

The risks associated with this study are small compared to the information that will be obtained. The information gathered may lead to major advances in our understanding of how to protect the emotional

health physical health of patients with lung cancer. If successful, it may enlarge our repertoire of methods for effectively enhancing the well-being of cancer patients.

#### Data Analysis & Statistical Considerations

Because this is a small pilot study with a small sample size power calculations are inappropriate. Below is a summary of the planned data analysis:

Descriptive statistics will be used to analyze SST-LC attendance, responses to questionnaire items, and sociodemographic data. Outcome measure data will be analyzed on an as per protocol basis. Standardized mean differences (with Hedges adjustment for small sample size) and 95% confidence intervals to examine the relative size of the intervention effect across the different measures. Scores are interpreted as positive intervention effects when the post-intervention values of negative affect are lower than baseline; and when post-intervention values of efficacy, affect, cognitive appraisal, coping, resilience, physical functioning and activity are higher than baseline. Psychological resilience and physical resilience self-report scores from baseline to 1-month follow-up will also be analyzed.

All quantitative analyses will be performed using IBM SPSS statistics software.

Participants enrolled in the study will complete participation across 2-4 months.

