## Purpose of the Study

This project will use Self-system therapy (SST), an empirically validated intervention based to treat depression and lung-cancer-related distress in older adults (65 years and older). We hypothesize that psychological measures and physical performance measures as indicators of resilience will be acceptable and feasible to participants.

(Hypothesis 1) Participants will complete at least 80% of SST treatment sessions (Hypothesis 2). There will be an association between measures of psychological and physical resilience. (Hypothesis 3). Lastly, we hypothesize that participant's psychological and physical resilience scores will improve from baseline to post-intervention as a function of receiving the SST intervention.

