#### Design & Procedures

Fifteen older adults (ages 65 and older) will be recruited from clinics of the Duke Cancer Institute.

Older adults with lung cancer will receive the SST intervention with sessions that range between 8 (recommended minimum number of sessions) to a maximum of 12 sessions lasting on average of 30-45 minutes. The intervention will be delivered by video conference. The design is a single-arm study, with no control or placebo group condition.

The four content/topic areas that are covered across the 8-12 SST intervention sessions are as follows:

1) Orientation Phase of SST. Participants are provided with a rationale for treatment that focuses on the importance of self-regulation for well-being in the context of advanced cancer.

2) Exploration Phase of SST. This phase consists of having patients examine successful and unsuccessful interpersonal interactions, functional difficulties, and their self-evaluations and goal pursuit strategies while coping with advanced cancer. Patients then identify and analyze their explicit or implicit preferences for certain kinds of personal goals.

3) Adaptation Phase of SST. The patient and interventionist work together to address each treatment goal, using change strategies and compensatory strategies that include helping the patient to modify goals or to learn to pursue them via different means that are a better fit to their current life circumstances, physical, limitations, or personality traits.

4) A maintenance plan is developed with each patient. The maintenance plan includes a list of strategies to be used daily (e.g. self-monitoring forms), short-term goals (e.g. becoming more active in self-rewarding activities) and long-term goals.

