#### Subject Recruitment

Potentially eligible candidates will be identified from each oncology provider's clinic schedules via medical chart review. This pre-identification process involves pre-screening of patients using their medical records on major characteristics (e.g., disease stage, current treatment status,) to reduce the unnecessary burden of contacting patients who will not screen in or of contacting patients who may be ill. Study staff will contact providers to obtain approval (as needed) to contact the potential participant. If the provider approves, a letter from the patient's provider will be sent to a candidate summarizing the research study. We will include a phone number for the patient to call to indicate that she is not interested in pursuing the study further.

A total of 15 patients will be recruited from Duke Cancer Center to complete study procedures.

Participants will have the opportunity to consent electronically via redcap database or by paper over the telephone. After completing a baseline assessment, participants will be sent sealed study materials along with the instructions regarding the study interventionist's name and contact information. All sessions will be conducted by trained interventionists with a Masters or doctoral degree in psychology or clinical social work and certified competent in the interventions by the PI. [name] will hold regular supervision sessions among the interventionists to ensure adequate quality of the delivered interventions. All supervision sessions are confidential; no identifiable information about participants is retained in supervision records.

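### The 80% session-completion hypothesis is the only one with a numerical bar, yet attendance is to be summarised without an interval; with 15 patients the observed figure is uncertain by roughly 11 to 17 points

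*Combined protocol and SAP*

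**What the plan says.** - **Target.** Purpose of the Study: "Participants will complete at least 80% of SST treatment sessions". The other hypotheses (acceptability and feasibility, association, improvement) carry no numerical threshold.
- **Attendance analysis.** Data Analysis & Statistical Considerations: "Descriptive statistics will be used to analyze SST-LC attendance, responses to questionnaire items, and sociodemographic data". No interval, decision rule or analysis population is given for attendance.
- **Where intervals are planned.** The same section: "Standardized mean differences (with Hedges adjustment for small sample size) and 95% confidence intervals to examine the relative size of the intervention effect". These concern the outcome measures.
- **Size and design.** Subject Recruitment: "A total of 15 patients will be recruited from Duke Cancer Center to complete study procedures". Design & Procedures: "The design is a single-arm study, with no control or placebo group condition". The analysis section adds: "Because this is a small pilot study with a small sample size power calculations are inappropriate".
- **Session count.** Design & Procedures: "sessions that range between 8 (recommended minimum number of sessions) to a maximum of 12 sessions". The plan does not say which number is the denominator of the 80%.

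**The concern.** The plan quantifies uncertainty where it sets no bar and omits it where it sets one. Because the 80% figure is framed as a hypothesis, the report will have to say something about whether it was supported. With no interval and no rule, the natural course is to set the observed percentage beside 80%. In 15 patients that comparison is imprecise, and a reader would have nothing to show how imprecise.

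A second problem is that a group mean can reach 80% while several patients attend few sessions or none. This pattern is plausible here: the patients have stage III-IV lung cancer, and the Risk/Benefit Assessment foresees withdrawal when health changes. A mean alone would not distinguish steady attendance across the group from full attendance by most and early loss of a few.

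**Working it through.** The plan gives no precision, power or error-rate figure for attendance, so there is nothing of its own to reproduce.

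**Inputs.** Bar 80% (Purpose of the Study); n = 15 (Subject Recruitment); 8 to 12 sessions (Design & Procedures). The between-patient SD of percentage attendance is an assumption, taken as 20, 25 and 30 points.

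**1. Precision of the mean.** Half-width = t(0.975, 14 df) × SD/√15, with t = 2.145 and √15 = 3.873.

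| Assumed SD | SE | 95% half-width | Interval around an observed 80% |
|---|---|---|---|
| 20 | 5.16 | 11.1 | 68.9% to 91.1% |
| 25 | 6.45 | 13.8 | 66.2% to 93.8% |
| 30 | 7.75 | 16.6 | 63.4% to 96.6% |

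**2. Chance that the observed mean reaches 80% when the true mean is lower.** Normal approximation: P = 1 − Φ((80 − μ)/SE).

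| True mean μ | SD 20 | SD 25 | SD 30 |
|---|---|---|---|
| 75% | 16.6% | 21.9% | 25.9% |
| 70% | 2.6% | 6.1% | 9.8% |
| 65% | 0.2% | 1.0% | 2.6% |

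**3. Cross-check with a different model.** A beta-binomial simulation of 15 patients with 8 sessions each, letting the within-patient correlation run from 0 to 0.7 (also an assumption), gives 12.1% to 33.4% at a true 75%, 0.9% to 17.7% at 70%, and from under 0.1% to 3.2% at 60%. With 12 sessions the figures are 7.0% to 32.4% at 75% and 0.2% to 17.0% at 70%. The message is the same: material at 75%, modest at 70%, slight at 60%.

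**4. What a mean can hide.** (12 × 100 + 3 × 0)/15 = 80%. Also (10 × 100 + 5 × 40)/15 = 80%.

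**5. Precision of a completer count.** If 12 of 15 patients each completed at least 80% of their sessions, the exact (Clopper-Pearson) 95% interval for that proportion is 51.9% to 95.7%.

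**6. The denominator.** A patient who attends 8 sessions scores 8/8 = 100% against the recommended minimum and 8/12 = 67% against the maximum. That 33-point gap is larger than any half-width in step 1. Reaching 80% takes 7 sessions out of 8 (0.8 × 8 = 6.4) but 10 out of 12 (0.8 × 12 = 9.6). No interval means anything until this is settled.

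**The case against.** The strongest case against is that this is a 15-patient pilot, for which a descriptive account of attendance is usual, and that descriptive statistics ordinarily include an SD, a range or a frequency table, which would expose the patterns in step 4. The second part has some force: the plan does not confine attendance to a mean, so the hidden non-completers are a risk of the wording and not a certainty. But the section names confidence intervals where it intends them, and attendance is not among those places. Nothing here asks for a power calculation or a test; an interval is a pilot-sized remedy that the plan already uses for its effect sizes.

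Some stronger readings are tempting but not supported:

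- A reader might infer that the hypothesis could easily be declared met with true attendance far below 80%. On the session-share reading, which is the more literal one, step 2 puts this at 2.6% to 9.8% for a true 70% and at most 2.6% for a true 65%.
- A reader might infer a formal pass/fail or go/no-go rule. None is stated. The Background links the pilot to a future larger RCT through its measures and their association, and does not mention attendance.
- A reader might infer that 80% of patients must be completers, and so that 15 patients could never confirm it, since even 15/15 has an exact two-sided lower limit of 78.2%. The protocol applies its 80% to sessions, not to patients.
- A reader might suppose that attendance is restricted to per-protocol patients. The text, "Outcome measure data will be analyzed on an as per protocol basis", applies that restriction only to outcome measures.

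**Conclusion.** The concern holds as a gap in reporting precision. The one hypothesis with a numerical bar has no planned interval, and with 15 patients an observed mean near 80% cannot be separated from values about 11 to 17 points lower. A true mean of 75% would reach the bar in about 17% to 26% of studies and a true 70% in about 3% to 10%.

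These sizes rest on the assumed SD of 20 to 30 points, on 15 analysed patients, on a normal approximation for a bounded quantity, and on reading the hypothesis as a mean share of sessions. The harm also supposes that the observed figure would simply be compared with 80%, which the plan neither states nor rules out. The undefined session denominator has to be resolved first. It is an inexpensive improvement worth making, not a flaw that invalidates the pilot.

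**What to change.** In Data Analysis & Statistical Considerations, keep the descriptive statistics for attendance and add the following:

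1. State one session denominator in advance, given that the design permits 8 to 12, and state that attendance is analysed over all enrolled participants.
2. Report the mean percentage of sessions completed with a 95% confidence interval, t-based or bootstrapped over participants, with limits held within 0 to 100%. An unrestricted t-interval can overshoot: 85 + 16.6 = 101.6.
3. Report the number and proportion of participants completing at least 80% of sessions, with an exact (Clopper-Pearson) 95% interval. Present this as an estimate, not as a comparison with a second 80% threshold.
4. Word the conclusion on the 80% session-completion hypothesis from the interval, and do not call it confirmed on the point estimate alone. Refer to it by content, because the placement of the hypothesis numbers in the Purpose of the Study is ambiguous.

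The cost is a few sentences and two simple intervals, with no extra patients, data or procedures. The downside is a more cautious stated conclusion.

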#### Risk/Benefit Assessment

Potential medical risks and discomforts: We do not anticipate any significant medical risks or discomforts to lung cancer patients who consent to participate in the study. Should the health status of a patient in a way that precludes further study participation, that participant will be able to withdraw from the study as needed (which will be stipulated in the consent form as per Duke University policy).

Potential psychological risks and discomforts: The study is not targeting treatment of psychiatric illnesses, and we do not anticipate that the participants will be at substantial risk of suicidality, self-harm, or harm to others. The PI is a licensed clinical psychologist and works in a research lab that has an in-place, IRB-approved procedure for the protection of research participants experiencing acute increases in distress which will be available throughout the duration of this project. All study staff will be trained in this existing procedure (which includes 24-hour phone access to the PI as needed).

A situation in which a study participant is at imminent risk of harming him/herself or others may necessitate involuntary reporting and intervention. This risk of loss of confidentiality will be discussed and disclosed to potential participants at the time of consenting. Because psychological interventions for emotional distress invariably require the patient to attend to discomfort and associated thoughts and

feeling, participation in the study will be associated with some risk of increased psychological distress, which may include discomfort with attention to unpleasant thoughts, feelings, or body sensations. Some individuals may experience an initial increase in undesirable feelings with increased attention to them. SST already contains procedures for identifying, anticipating, and minimizing discomforts that often characterize psychotherapy and related preventive interventions, and the interventionists will be thoroughly trained in how to use those techniques to simultaneously protect participants and assist them in gaining benefit from the intervention.

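### Per protocol is undefined and is the only analysis set for outcomes, so patients who miss sessions but could still be assessed may be dropped from an uncontrolled before-after change

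*Combined protocol and SAP*

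**What the plan says.** The Data Analysis & Statistical Considerations section gives one basis for outcomes: "Outcome measure data will be analyzed on an as per protocol basis". No session count, assessment requirement or deviation rule defines the set. No all-enrolled or all-available-data outcome analysis is named, and there is no missing-data rule.

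Two attendance figures appear elsewhere, and neither is tied to the analysis set. Purpose of the Study hypothesises: "Participants will complete at least 80% of SST treatment sessions". Design & Procedures describes a course of "8 (recommended minimum number of sessions) to a maximum of 12 sessions".

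On design and interpretation:
- Design & Procedures: "The design is a single-arm study, with no control or placebo group condition".
- Purpose of the Study, last hypothesis: participants' "psychological and physical resilience scores will improve from baseline to post-intervention as a function of receiving the SST intervention".
- Data Analysis: "Scores are interpreted as positive intervention effects when the post-intervention values of negative affect are lower than baseline", with rises in the other measures read the same way.
- Data Analysis: "Psychological resilience and physical resilience self-report scores from baseline to 1-month follow-up will also be analyzed". No further method is given for these scores.

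Risk/Benefit Assessment foresees a change in health that "precludes further study participation, that participant will be able to withdraw from the study as needed". Nothing says whether a patient who stops sessions but stays in the study is still assessed.

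**The concern.** There are two linked problems. First, an undefined set can be settled after the data are seen, and with 15 patients each exclusion is 1/15 = 6.7% of the sample. Second, the usual meaning of per protocol removes patients for missing sessions even when their post-intervention scores could be collected.

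With no control arm, the before-after change is the only effect estimate, so selection on attendance enters it directly. If patients stop because their health worsens, which is plausible in stage III-IV lung cancer but not shown by the document, those left in are the ones doing better and the change is biased towards improvement. If stopping is unrelated to outcome there is no bias. If improvers stop early, the bias runs the other way. The planned attendance summary would show who fell short, but not why or how their scores changed. The same set would apply to the 1-month self-report resilience scores.

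Patients who withdraw from the study or die give no later data under any analysis set. That loss is separate and is not caused by choosing per protocol.

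**Working it through.** The plan gives no attrition rate, SD or expected effect, so there is no figure of its own to reproduce. From the document: N = 15, one arm, 8 to 12 sessions, an 80% attendance hypothesis, standardised mean differences with 95% confidence intervals. Everything marked as assumed below is an illustration.

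**1. Do the two attendance figures give one rule?** The 80% cut-off for s planned sessions is 0.8 × s, rounded up.

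| Planned sessions | 0.8 × s | Needed for 80% | Cases where 80% and the minimum of 8 disagree |
|---|---|---|---|
| 8 | 6.4 | 7 | 7 of 8 (87.5%): meets 80%, not the minimum |
| 9 | 7.2 | 8 | none |
| 10 | 8.0 | 8 | none |
| 11 | 8.8 | 9 | 8 of 11 (72.7%): meets the minimum, not 80% |
| 12 | 9.6 | 10 | 8 of 12 (66.7%) and 9 of 12 (75%): meet the minimum, not 80% |

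Four cases are classified differently, given a planned number of sessions for each patient.

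**2. How far could the per-protocol mean move?** Assumed: change and propensity to stay are bivariate normal, true mean change is zero, and the k of 15 patients with the lowest propensity stop sessions. Per-protocol mean minus the mean of all 15, in SD of change (simulation, 400,000 runs):

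| k who stop | corr 0.3 | corr 0.5 | corr 0 | corr -0.3 |
|---|---|---|---|---|
| 3 | 0.098 | 0.164 | 0.00 | -0.099 |
| 5 | 0.154 | 0.258 | 0.00 | -0.155 |
| 6 | 0.182 | 0.306 | 0.00 | -0.184 |

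Large-sample check, corr × φ(z_d)/(1 − d) with d the fraction stopping: d = 1/5 gives 0.105 and 0.175; d = 1/3 gives 0.164 and 0.273; d = 2/5 gives 0.193 and 0.322 (corr 0.3 and 0.5). These are close to the simulated values.

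**3. How much could a different set recover?** Only what comes from stoppers who can still be assessed. If m of the k are assessed, the recoverable part is the per-protocol mean minus the all-available mean. Low end: corr 0.3, with the lowest-propensity stoppers unassessed. High end: corr 0.5, with a random m assessed.

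| k stop | m assessed | Recoverable, SD of change |
|---|---|---|
| 3 or 6 | 0 | 0 |
| 3 | 1 | 0.030 to 0.063 |
| 3 | 2 | 0.061 to 0.117 |
| 6 | 2 | 0.056 to 0.139 |
| 6 | 4 | 0.114 to 0.235 |

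The high end can be checked by hand. For k = 3 the stoppers average −(12/3) × 0.164 = −0.656, so with two assessed the shift is 2/14 × (0.164 + 0.656) = 0.117. For k = 6 they average −(9/6) × 0.306 = −0.459, so with four assessed it is 4/13 × (0.306 + 0.459) = 0.235.

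**4. Scale.** The plan does not state the standardiser. With an assumed pre-post correlation of 0.7, SD of change = √(2 × (1 − 0.7)) = 0.775 baseline SD, so 0.10-0.31 becomes 0.08-0.24 baseline SD. The 95% CI half-width in SD of change is t/√n: 0.635 at n = 12 and 0.769 at n = 9. The full shift is therefore 0.098/0.635 = 15% to 0.306/0.769 = 40% of the half-width. The interval reflects sampling error only and would not reveal the shift.

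**5. Break-even.** The overall mean is zero when those lost average −(observed mean × number observed)/number lost. For an assumed observed mean of +0.30 SD: with 6 lost, −0.30 × 9/6 = −0.45 SD; with 2 lost, −0.30 × 13/2 = −1.95 SD. The first is a modest decline and the second a large one, so the number lost matters a good deal to how far a favourable mean can be trusted.

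**The case against.** The wording may only mean that outcomes are analysed as the protocol sets out, in which case nobody is excluded for missed sessions. That reading is possible; it is why the claim is that patients may be dropped, and it confirms that the phrase needs defining.

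The section also plans descriptive statistics of questionnaire responses with no stated restriction. These could include patients who missed sessions, but they are not a baseline-to-post effect estimate.

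The four discordant session cases need a planned number for each patient. If course length is flexible, a patient who stops at 8 may have completed 8 of 8. This stands as a limit: the cases show ambiguity, not contradiction.

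The size is wholly assumed, its sign is unknown, and it is smaller than the confidence interval half-width. This also stands. Confidence is high about the missing definition and the sole analysis set, not about the amount of bias.

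Finally, this is a 15-patient pilot whose before-after change cannot be attributed to SST under any set, and a treated set is a defensible choice. True, but the plan commits to effect sizes with intervals and reads their direction as intervention effects. A wider set removes one avoidable distortion, and per protocol can remain as a secondary set.

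**Conclusion.** The concern holds. Per protocol is undefined, it is the only analysis set named for outcomes, and following it in its usual sense can exclude assessable patients from the only effect estimate in an uncontrolled study. The plausible direction is towards improvement, but the document does not establish it.

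Under the stated assumptions the distortion is 0.10 to 0.31 SD of change, which is an upper bound on what changing the set can recover. The recoverable part is 0.06-0.12 SD (3 stop) or 0.11-0.24 SD (6 stop) if two thirds of those who stop can be assessed, 0.03-0.06 or 0.06-0.14 SD if one third can, and zero if none can. At zero correlation there is no bias; at −0.3 the upper bound becomes −0.10 to −0.18 SD. This should be fixed because the remedy is cheap and scores not collected when due cannot be recovered later.

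**What to change.** 1. Make the main outcome analysis all enrolled participants with a baseline, using all available post-intervention data and 1-month self-report resilience data, whatever the number of sessions attended.
2. Request these already planned assessments, when they fall due, from participants who stop sessions but remain willing and able.
3. Report the number lost and the reasons, by measure and time point, with the break-even mean change among those lost.
4. If per protocol is kept, define it before the data are seen by one session rule that works for every planned length from 8 to 12, and label it secondary.

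The cost is a short paragraph in the analysis section, a little operational work to seek the planned assessments, and one line of arithmetic per measure. No larger sample is needed. The estimate may come out smaller, and bias from patients with no later data remains: the break-even value can show how much it would matter but cannot remove it.

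### Does leaving the standardising SD unnamed undermine the comparison of effect sizes across measures?

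*Combined protocol and SAP*

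**What the plan says.** The Data Analysis & Statistical Considerations section calls for "Standardized mean differences (with Hedges adjustment for small sample size) and 95% confidence intervals to examine the relative size of the intervention effect", and the same sentence makes clear that the comparison runs from one measure to another. It then gives one rule of interpretation, which concerns direction. A fall in negative affect counts as a positive effect, and so does a result where "post-intervention values of efficacy, affect, cognitive appraisal, coping, resilience, physical functioning and activity are higher than baseline". Together these make eight domains.

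Design & Procedures states: "The design is a single-arm study, with no control or placebo group condition". Every effect is therefore a change within the same participants. Subject Recruitment gives the size: "A total of 15 patients will be recruited from Duke Cancer Center to complete study procedures".

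No section says which SD divides the mean change. The Hedges adjustment is a small-sample multiplier and does not settle this, and neither does naming SPSS as the software. The data analysis section also says that resilience "self-report scores from baseline to 1-month follow-up will also be analyzed", but not that this follow-up analysis uses standardised differences.

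**The concern.** For a paired change, at least three divisors are in ordinary use: the baseline SD, the average of the baseline and post SDs, and the SD of the individual changes. The first two express the shift relative to the spread between people. The third expresses it relative to how uniformly people changed, so it depends on the pre-post correlation of each measure. If correlations differ between measures, the same data can yield two tables in which the measures are ordered differently.

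That bears on the one purpose the plan gives these effect sizes. The domains are varied, and the Purpose of the Study speaks of "psychological measures and physical performance measures as indicators of resilience", so a single common correlation cannot be presumed. Two analysts following the same text could disagree about which measure moved most. An analyst who chose the divisor after seeing the data could, even without meaning to, favour one measure.

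**Working it through.** **Inputs.** n=15 and the single-arm design come from the protocol. The documents give no effect size, SD or correlation, so there is no planned figure to reproduce, and every shift and correlation r below is an assumption. Baseline and post SDs are taken as equal.

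**Formulas.**
- Hedges factor: J = 1 − 3/(4·df − 1). With df = 14, J = 1 − 3/55 = 0.945.
- On the baseline SD: g = J × d, where d is the shift in baseline SDs.
- On the SD of change: g = J × d / √(2(1 − r)).

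J is the same for all measures with the same n, so it cannot alter the order. The conversion factor 1/√(2(1 − r)) can:

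| r | 0.3 | 0.5 | 0.7 | 0.8 | 0.9 |
|---|---|---|---|---|---|
| factor | 0.85 | 1.00 | 1.29 | 1.58 | 2.24 |

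**A reversal.** Measure A shifts 0.50 SD with r=0.5; measure B shifts 0.40 SD with r=0.8.
- Baseline SD: A = 0.945 × 0.50 = 0.47; B = 0.945 × 0.40 = 0.38.
- SD of change: A = 0.47 × 1.00 = 0.47; B = 0.38 × 1.58 = 0.60.

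The order flips once r for B exceeds 1 − (0.40/0.50)² × (1 − 0.5) = 0.68.

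**What does not change.** The numerator is the same mean paired change and each divisor is positive, so the sign is the same under all three. On the SD-of-change scale the 95% intervals (noncentral t) are −0.04 to 0.97 for A and 0.06 to 1.12 for B. Rescaled to the baseline SD, treating the ratio of SDs as known, A is unchanged and B is 0.04 to 0.71. On either scale A's interval includes zero, B's excludes it, and the two overlap almost entirely.

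**How often the table would differ.** Simulated trials with n=15, eight measures, normal data, true shifts spread over 0.1 to 0.5 SD and between-measure correlation 0.3. The share of trials in which baseline SD and SD of change name a different largest effect:

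| spread of r across measures | share |
|---|---|
| 0.3 to 0.9 | 58% |
| 0.5 to 0.8 | 44% |
| all 0.7 | 39% |

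The last row has no difference in correlation at all, so 39% is sampling noise. A spread of 0.5 to 0.8 adds 44 − 39 = 5 percentage points. The larger addition, 58 − 39 = 19 points, needs the widest assumed spread. The two divisors based on raw-score SDs (baseline and average) differ on the largest effect in 16–18% of trials.

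**What naming a divisor would buy.** In the same spread-shift setting, with the baseline SD fixed in advance, the top-ranked measure is truly the largest in about 35% of trials, and an identical repeat trial names a different one about 77% of the time. With the SD of change fixed in advance, a repeat differs in 60–76%.

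**The case for a change.** The strongest case for a change is that the effect-size table is the main quantitative output on change, since the plan has no power target. The Background section also looks ahead to a larger randomised trial, so a reader may use the table to see which measures responded. An unnamed divisor adds variation that is avoidable and separate from sampling error, and one sentence would remove it. To say that the analyst will choose sensibly is no full answer, because all the choices are sensible.

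Part of this stands. The divisor is missing, the algebra is right, and naming it would make two analysts agree. What does not stand is that the plan leads to a wrong result without it. The plan speaks of relative size; it does not rank measures or pick a winner, and its only rule of interpretation is direction, which no divisor changes. None of the stated hypotheses (acceptability and feasibility, session completion, association between psychological and physical resilience, improvement from baseline) turns on the order of effects. The future trial is mentioned in connection with prediction models, not with choosing outcomes by effect size.

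Two further worries fall away. The plan does not place the 1-month scores in the standardised comparison. In a single-arm design the ordinary reading of the confidence intervals is that they are paired, so a two-group formula is not a realistic risk.

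**Conclusion.** The gap is genuine but calls for no change. An analyst who uses any ordinary paired divisor consistently, and states it with the results, delivers what the plan promises: a descriptive table of how far each measure moved, with intervals. If the raw mean change and the pre-post correlation are shown as well, readers can convert approximately from one scale to the other.

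The choice can move a single effect materially (0.38 against 0.60 in the example) and can reverse an order. However, the order from 15 participants is unreliable whichever SD is used, and nothing in the plan is decided by it. Fixing the divisor in advance would secure agreement between analysts, not a trustworthy ranking. These sizes rest on assumed shifts of 0.1 to 0.5 SD, assumed correlations of 0.3 to 0.9, normal data, equal SDs and all 15 participants contributing. The conclusion itself rests on the absence of any rule tied to the order. It would need another look if the ranking were used to select outcomes for the later trial.
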